Timing of Assessments: Initial evaluations will be performed \leq 14 days before starting natural progesterone. Subsequent evaluations will be at the following time points after initiation of study therapy (4 weeks \pm 3 days, 8 weeks \pm 1 week, 24 weeks \pm 2 weeks) with one final off-study evaluation if it is prior to the 24 week evaluation and $>$ 2 weeks from previous evaluation (this evaluation would be the visit when patient comes off study).

QOL Questionnaires: EORTC Quality of Life Questionnaire-Core 30/Brain Cancer Module-20 (EORTCQLQ30/BN20); M. D. Anderson Symptom Inventory Brain Tumor Module (MDASI-BT)

2. Objectives (and Endpoints)

Our main goal is to establish pharmacokinetics, safety/tolerability and efficacy of daily subcutaneous natural progesterone for the treatment of patients with recurrent glioblastoma. The specific objectives/endpoints of this study are listed below.

OBJECTIVES	ENDPOINTS
Primary	

Protocol Title: Pilot study of progesterone for recurrent GBM

OBJECTIVES	ENDPOINTS

To determine that the pharmacokinetics of natural progesterone given to recurrent GBM patients by subcutaneous injection is consistent with previous determinations made using the aqueous formulation of progesterone (IBSA Institut Biochimique SA, Lugano, Switzerland) given subcutaneously.To determine the safety of administering daily subcutaneous natural progesterone for the treatment of patients with recurrent GBMs.To determine the ORR [defined as stable disease (SD) or better (PR or CR)] at 8 weeks in eligible patients with recurrent GBM treated with daily subcutaneous natural progesterone.	
Pharmacokinetic: Plasma progesterone levels at 0, 30 min, 1, 2, 4, 6, 8 hrs from 1st injection and at 8 prior to drug injection in 3 pts at each dose level. (May alternatively be done on any day after the 1st week during the initial 4 weeks with no need for day 8 trough draw if done later)Safety: Adverse events, clinical assessments (eg. vital sign, physical, etc.), clinical laboratory test.Efficacy: Overall response rate (ORR) per protocol volumetric definition at 8 weeks from initiation of progesterone.
Secondary	

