- **Partial Response (PR):** (Measurable disease only) Greater than or equal to 65% decrease under baseline in total tumor volume of all measurable lesions. No progression of non-evaluable disease (defined as progression to at least 1.5 cm^3 in volume). No new lesions. All measurable lesions and sites must be assessed using the same techniques as baseline. If there is only non-evaluable disease or no enhancing disease present at baseline, then this criteria will not apply and the case will not be considered in the N when evaluating for % of patient achieving PR.
- **Stable Disease (SD):** Does not qualify for CR, PR, or progression. The designation of SD requires a minimum of 8 weeks duration (2 assessment of stable disease from baseline at least 4 weeks apart). All measurable sites must be assessed using the same techniques as baseline. The steroid dose at the time of the scan evaluation should be no greater than the maximum dose used in the first 8 weeks from initiation of therapy.
- **Progressive Disease (PD):** 40% increase in the tumor volume of all measurable lesions over previous exam (over baseline if no decrease) using the same techniques as baseline, OR clear progression of non-evaluable disease (defined as growth to at least 1.5 cm^3 in volume), OR clear appearance of any new measurable lesion/site, OR clear clinical worsening or failure to return for evaluation due to death or deteriorating condition (unless clearly unrelated to this cancer).

Best Response: This will be calculated from the sequence of objective statuses. For patients with all disease sites assessed every evaluation period, the best response will be defined as the best objective status as measured according to the above criteria.

Pharmacokinetic Testing (Research)

Protocol Title: Pilot study of progesterone for recurrent GBM

Number of patients tested: The first three patients of a treatment dose level will be undergo pharmacokinetic testing for plasma level of progesterone.

Timing of Assessments: Pharmacokinetic samples will be obtained on day 1 of therapy. Plasma samples will

be obtained immediately prior to administration of drug and, subsequently, at 30 minutes, 1 hour, 2 hour, 4 hours, 6 hours, and 8 hours after drug injection. Additional sample will be obtained prior to the day 8 injection. (May alternatively be done on any day after the 1st week during the initial 4 weeks with no need for day 8 trough draw if done later)

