- **MGMT methylation** – This will be determined by methylation-specific PCR with results reported as positive, negative or borderline. All patients originally diagnosed at Emory has this test performed as part of the routine neuropathologic assessment. Will plan to use results from original pathology report unless it was not performed in which case the original tumor tissue block will be obtained for this testing [Atif et al. 2019].
- **Mutations in the following genes (p53, EGFR, PTEN, AKT, IDH1, IDH2)** – Sequence variation at hotspots within these genes will be assessed via a SnapShot Cancer Mutation Panel. All patients originally diagnosed at Emory have this test performed as part of the routine neuropathologic assessment. We plan to use results from the original pathology report unless it was not performed; in which case, the original tumor tissue block will be obtained for this testing [Atif et al. 2015a; Atif et al. 2015b; Atif et al. 2019].
- **Genomic loss/gain particularly at the following loci (1p, 1q, 7p, 10q, 19q)** – Copy number variation of the entire genome will be assessed via the Oncoscan SNP Microarray Analysis. All patients originally diagnosed at Emory have this test performed as part of their routine neuropathologic

assessment. We will use results from the original pathology report unless it was not performed in which case the original tumor tissue block will be obtained for this testing.

Potential serum biomarkers (Research)

We propose to test a panel of circulating biomarkers to evaluate the effect of progesterone treatment on glioblastoma progression. The levels of these proposed biomarkers have been correlated with glioblastoma progression and survival in a number of clinical studies.

Serum will be obtained within 14 days prior to the start of treatment and at the 4 weeks blood draws after initiation of treatment. The initial and changes in levels of these biomarkers will be correlated with outcomes of patients on study to determine if there are detectable associations with response to progesterone. ELISA or Multiplexed fluorescent microsphere immunoassay will be performed to measure the levels of the following biomarkers:

- YKL-40 [Hormigo et al. 2006; Iwamoto et al. 2011]
- Matrix Metalloproteinase-9 (MMP-9) [Hormigo et al. 2006]
- Glial Fibrillary Acidic Protein (GFAP) [Jung et al. 2007]
- C-Reactive Protein (CRP) [Strojnink et al. 2014]
- Soluble CD14 [Zhou et al. 2010]
- Soluble CD23 [Zhou et al. 2010]

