15.1 Statistical consideration section: Biostatistician

This is a single arm, Phase 1 study, designed to evaluate the pharmacokinetics, safety/tolerability and efficacy of subcutaneously administer natural progesterone in subjects with recurrent glioblastoma (GBM). The study consists of two parts: Part 1) Dose finding phase; Part 2) Dose expansion phase.

Statistical design and sample size:

Dose finding phase (Part 1):

The dose finding phase will proceed using a standard 3+3 approach in order to identify the maximum tolerated dose (MTD). The study will start at Dose Level 0 with dose moving according to protocol criteria

Protocol Title: Pilot study of progesterone for recurrent GBM

(Section 5.2). For the 3+3 dose finding phase, a dose limiting toxicity (DLT) will be defined as a grade 3 or

greater toxicity that is not clearly due to the underlying disease or extraneous causes that develops in the first 28 days of starting progesterone (exceptions as noted in **Section 5.3**). Dose levels are shown on the following table:

Dose Level	Daily subcutaneous dose (mg)
-1	25
0	50
1	75

After treatment initiation of up to 6 patients at a dose level and continuation for a minimum of 4 weeks with AE assessment, enrollment to the next (higher or lower) dose level as determined by the rules will only start after data is presented to the Winship Data Safety Monitoring Committee (DSMC) and final approval is obtained for starting the next dose level. The sample size in the dose finding phase will range from 6-12.

Dose expansion phase (Part 2):

A total of 20 patients will be enrolled at the MTD (including those in the Dose finding phase at this dose level) in the dose expansion phase unless futility criteria for the expansion cohort is met. The MTD from the dose finding phase (25 mg, 50 mg, or 75 mg) administered subcutaneously 1x/day will be given in this expansion cohort until 20 patients have initiated the dose determined from the dose finding phase. The objective of the dose expansion phase is to provide a preliminary efficacy assessment, and thus no further justification for this sample size is required.

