- To determine and compare the overall survival of eligible patients with recurrent GBM. Patients on this study will be followed for overall survival (OS) which is defined from the time of pre-treatment MRI to the time of death. Both actuarial OS curves and 24-week OS (for expansion dose patients and all patients as separate analyses) will be estimated using the Kaplan-Meier method, and compared to matched historical controls using log-rank tests and univariate Cox proportional hazards models. The matched effects will be estimated by a Cox model with a robust variance estimator. A 95% confidence interval will be provided for 24-week OS using the Greenwood formula to estimate the standard error.

Exploratory Objectives:

Dose expansion phase (Part 2):

- To determine whether progesterone receptor levels within the tumor correlates with response to daily subcutaneous natural progesterone. This will be examined for both expansion dose patient and all patients as separate analyses. Original tumor and any recurrent tumor samples will be assessed for progesterone receptor expression levels by immunohistochemistry and these results will be correlated with response assessment to determine whether there is any correlation. Progesterone receptor staining by IHC will be scored on a scale of 0-4 by standard criteria and then compared with response assessment using standard statistical tests such as two sample t-tests or Mann-Whitney U tests, where appropriate, to determine whether there is any correlation between expression level and response.
- To determine if other intrinsic tumor factors (mutations and genomic loss/gains, see **Section 5.7** for specific details) correlates with response to daily subcutaneous natural progesterone. This will be examined for both expansion dose patient and all patients as separate analyses. Each of the tumor mutational and genomic loss/gain factors will be scored and these results will be correlated with response assessment using chi-square tests or Fisher's exact tests, where appropriate.

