- To determine if the absolute values or changes in the level of serum biomarkers (see **Section 5.7** for specific biomarkers) correlates with response to daily subcutaneous natural progesterone. This will be examined for both expansion dose patient and all patients as separate analyses. Each of these serum biomarkers will be quantitated at the specific time points (pre-treatment and 4 weeks) with specific levels and changes in levels recorded. These results will be correlated with response assessment using two sample t-tests or Mann-Whitney U tests, where appropriate.
- To determine the quality-of-life (QOL) by validated instruments of eligible patients with recurrent GBM. This will be examined for both expansion dose patient and all patients as separate analyses. Serial QOL assessments will be determined in patients and compared with historical cohorts to determine whether there is any difference in patients treated with subcutaneous progesterone for recurrent GBM. Linear mixed effects models will be applied to model the repeatedly measured score from each assessment and/or test over time. We hypothesize that response to progesterone will correlate with positive effects on the temporal changing patterns in the scores on the QOL assessments. We will follow the recent guidelines of the American Statistical Association on reporting p-values and their meaning [Wasserstein and Lazar 2016; Wasserstein et al. 2019]

Safety assessment:

Adverse event stopping rule including interim analysis: Safety assessments will be performed throughout treatment, at weekly intervals during the 1st 4 weeks and at the beginning of every 4 weeks interval thereafter until patient comes off study. In the dose finding phase, stopping rules are described above. Besides the toxicity assessment of 3-6 patients at a dose level in the dose finding phase, toxicity will be assessed during the dose expansion phase on an ongoing basis. If, at any time, the aggregate rate of treatment-related toxicities meeting DLT criteria exceeds 33% across all subjects treated in the expansion cohort, the findings will be discussed and further enrollment may be interrupted. Depending on the nature and grade of the toxicity and after assessing the risk:benefit ratio, a new dose(s) for all cohorts may be initiated at a previously tested lower dose level, or at a dose level intermediate to previously tested lower dose levels.

15.2 Data/specimens:

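### The exploratory marker tests cannot distinguish a marker of progesterone benefit from a marker of prognosis, although the objectives word any association as response to progesterone

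*Combined protocol and SAP*

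**What the plan says.** Section 15.1 describes the design: "This is a single arm, Phase 1 study, designed to evaluate the pharmacokinetics, safety/tolerability and efficacy". Section 2 sets the response endpoint: "To determine the ORR [defined as stable disease (SD) or better (PR or CR)] at 8 weeks".

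The exploratory objectives in Sections 1.1, 2 and 15.1 ask whether each marker is related to response to the study drug. The planned tests are:

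- Progesterone receptor score (0-4): compared with response "using standard statistical tests such as two sample t-tests or Mann-Whitney U tests, where appropriate".
- Mutations and copy-number changes: "these results will be correlated with response assessment using chi-square tests or Fisher's exact tests, where appropriate".
- Six serum markers, before treatment and at 4 weeks, as levels and changes: "These results will be correlated with response assessment using two sample t-tests or Mann-Whitney U tests, where appropriate".

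Each is run in expansion-dose patients and in all patients. Section 15.1 uses matched historical controls for PFS and OS and historical cohorts for quality of life, but no comparison group for any marker analysis. Of the serum markers, Section 5.7 says: "The levels of these proposed biomarkers have been correlated with glioblastoma progression and survival in a number of clinical studies".

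**The concern.** The tests ask whether the marker is related to remaining progression-free in patients who all receive progesterone. The objectives ask whether it is related to what progesterone does. With no comparison group the second question has no data behind it. A marker of slower-growing tumor would separate responders from non-responders even if the drug were inert, and the plan's own words would then describe it as related to response to progesterone. The risk is a mistaken claim of drug sensitivity that might be carried into a later trial.

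The week-4 serum values have a further difficulty. They are scheduled at day 29, as is the week-4 MRI. A patient already progressing on that MRI cannot be stable, so the comparison is partly between blood drawn at progression and blood drawn without it.

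**Working it through.** The plan gives no alpha, effect size or power for the marker tests, so there is no figure to reproduce. A two-sided 5% level is assumed throughout.

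**1. What the test sees.** Let p1(m) be the response probability on progesterone at marker value m, and p0(m) the probability without it. The planned null is that p1(m) is constant. The claim in the objectives concerns the contrast between p1(m) and p0(m). The trial estimates only p1. If the drug is inert, p1 = p0, and the test rejects whenever p0 varies with m.

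Example with a binary marker, 10 patients per group (50% prevalence assumed). With response 60% v 10%, Fisher's test rejects 47% of the time; with 40% v 10%, 15%. These rates are the same whether the difference is prognosis or a drug effect confined to marker-positive patients.

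**2. Inputs from Section 15.1.** Ineffective therapy may give a 10% response rate. The expansion-dose set is 20. Enrollment stops if at most 1 of the first 10 responds. At 10%, P(2 or more of 10) = 1 - 0.9^10 - 10(0.1)(0.9^9) = 1 - 0.349 - 0.387 = 0.264, so the trial stops 73.6% of the time. With 1 responder in 10, the smallest exact two-sided Mann-Whitney p is 2/10 = 0.20.

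**3. Inert drug, purely prognostic baseline marker.** Progression is taken as exponential and m as standard normal. P(no progression at 8 weeks) = S^(HR^m), where S is the rate at the mean marker value. With S = 0.10 and HR = 2, a patient one SD below the mean has 0.10^0.5 = 0.32 and one SD above has 0.10^2 = 0.01. Mann-Whitney rejection over 4000 simulated trials:

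| No-drug setting | HR 1.5 | HR 2.0 | HR 2.5 |
|---|---|---|---|
| 10% at mean marker, interim stop applied | about 8% | about 24% | about 36% |
| 10% at mean marker, all 20 enrolled | 16% | 37% | 54% |
| 20-50% at mean marker, all 20 enrolled | about 20% | about 44% | about 63% |
| 10% averaged over patients, interim stop applied | about 7% | about 13% | about 17% |

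Repeat runs differ by one or two percentage points. With 20 enrolled and a no-drug rate of 20-50%, a marker that is not prognostic rejects 4-5% of the time.

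**4. Week-4 serum.** Section 5.7 states: "The designation of SD requires a minimum of 8 weeks duration (2 assessment of stable disease from baseline at least 4 weeks apart". A patient with PD at week 4 therefore cannot be SD at week 8. Assume weekly log-volume growth distributed N(0.09, 0.10) and PD at a 40% increase (ln 1.4 = 0.336).

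- Not PD at week 4: growth below 0.336/4 = 0.084, probability Φ(-0.06) = 0.48, or 9 to 10 of 20.
- Not PD at week 8: growth below 0.336/8 = 0.042, probability Φ(-0.48) = 0.32.
- For a 10% week-8 rate the mean growth must be 0.042 + 0.128 = 0.170. Then Φ(-0.86) = 0.195, or about 4 of 20, remain at week 4.

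Under the first growth setting, a serum change that tracks volume with signal 0.5 or 1.0 times the noise rejects about 29% or 71-75% of the time in all 20 patients. Among those not progressing at week 4 it rejects 4% or 10%. Part of that fall is only the smaller sample and narrower range of growth.

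**The case against.** The best defence is the expectation in Section 15.1 that enhancing recurrences all progress without effective therapy. If that held, every stable patient would show drug effect. It conflicts with the 10% rate for ineffective therapy in the same section. Nor does it cover patients enrolled after resection with no minimum residual disease (Section 9), or isolate progesterone in patients continuing bevacizumab.

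Several other points stand. These are exploratory analyses in a pilot, described as correlations, with American Statistical Association guidance on p-values cited. The limitation is inherent to a single arm. The statement about known links to outcome covers the six serum markers only; the tumor markers are tied to preclinical pathways. None of this changes what the tests compare or how the objectives are worded.

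A reader might infer that every prognostic marker will be reported as a progesterone marker. The documents do not support that: at their 10% rate with the interim stop, most such markers would miss significance. A reader might also take the tests to be fixed at 8 weeks. Section 15.1 refers to response assessment without a time point, and Section 5.7 also defines best response and speaks of patient outcomes; every reading stays within treated patients. Nor does any section plan to select patients by marker.

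A marker-by-cohort interaction against the historical controls looks like a remedy but is not a sound basis for claims. Those controls received a range of therapies, and Section 3.1 itself links MGMT to temozolomide resistance, so an interaction could reflect the control treatment. Controls are not stated to be Emory patients with routine molecular results, and may not share the volumetric progression criteria. Power is low: about 22% for an interaction hazard ratio of 0.5 with 20 trial patients, 40 controls, 40% prevalence and all events observed.

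**Conclusion.** The point holds in this form: any marker association found in this trial cannot be separated from prognosis, and nothing in the documents permits attributing it to progesterone as the objectives do. That follows from the design and needs no simulation.

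How often a prognostic marker would reach significance with an inert drug rests on assumption: about 8% to 36% at the plan's 10% rate (at the mean marker value) with the interim stop, and about 20% to 63% if the no-drug rate is 20-50% and 20 patients are enrolled. The hazard ratios, exponential model and 5% level are assumed. The higher rates are possible given resected and bevacizumab-treated patients, but are not stated in the plan. The separate all-patients analysis is not in these figures and would add some patients.

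The week-4 overlap is real by schedule, though the draw and scan need not fall on the same day: serum has a window of ±3 days, while Section 5.6 allows ±1 week for that MRI. This is a minor, worthwhile correction to an exploratory analysis.

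**What to change.** 1. In Sections 1.1, 2 and 15.1, reword the progesterone receptor, mutation/copy-number and serum objectives as *associated with disease control in treated patients; prognostic and predictive effects not separable*.
2. State in Section 15.1 that no conclusion about progesterone sensitivity or patient selection will be drawn from these tests alone.
3. For week-4 serum levels and changes, state that patients with PD on the week-4 MRI are non-responders by definition. Keep the planned comparison and add a sensitivity analysis limited to patients without progression at week 4, reported descriptively because few will remain (roughly 4 to 10 of 20 in the model above).
4. Do not use a marker-by-historical-control interaction as the basis for statements about progesterone.

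The cost is wording and one extra descriptive table, with no new data or patients. The price is a more modest claim and a sensitivity analysis too small to settle the question.

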1-2 of 6 with DLT → **expand Level 1 to 20 patients**
3-4 of 6 with DLT → **expand Level 0 to 20 patients**
2-3 of 3 with DLT → **expand Level 0 to 20 patients**

During the dose finding phase of the study, a treatment will be considered safe/tolerable if no DLT defined as \geq grade 3 toxicity during the first 4 weeks drug therapy not clearly due to the underlying disease or extraneous causes with exceptions as noted in **Section 5.3**. After treatment initiation of up to 6 patients at a dose level and continuation for a minimum of 4 weeks with AE assessment, enrollment to the next (higher or lower) dose level as determined by the rules will only start after data is presented to the Winship Data Safety Monitoring Committee (DSMC) and final approval is obtained for starting the next dose level.

Dose escalations will be reviewed by the Winship Data Safety Monitoring Committee (DSMC) (per Winship SOP 7.9 Dose Escalation Determinations for Sponsor-Investigator or Investigator Initiated Studies). The PI or designee will provide an update on all relevant safety data of patients entered to a dose level to the DSMC when dose escalation is planned. Upon obtaining approval from the DSMC, dose escalation can proceed.

Dose Expansion Phase (Part 2):

The purpose of cohort expansion is to gather additional safety and tolerability information, and evaluate the efficacy of aqueous natural progesterone for injection at the dose determined by the Dose Finding Phase of the study.

The PI or designee must provide the DSMC a report outlining the overall enrollment and path to decision for the escalation dose(s) selected.

Continuous evaluation of toxicity events in the cohort expansion will be performed throughout enrollment in the expansion cohort. If, at any time, the aggregate rate of treatment-related toxicities meeting DLT criteria exceeds 33% across all subjects treated in the expansion cohort, the findings will be discussed and further enrollment may be interrupted. Depending on the nature and grade of the toxicity and after assessing the risk:benefit ratio, a new dose(s) for all cohorts may be initiated at a previously tested lower dose level, or at a dose level intermediate to previously tested lower dose levels.

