5.3 Definition of Dose-Limiting Toxicity

The safety of this approach will be confirmed by assessing toxicity potentially attributable to the daily progesterone treatment. National Cancer Institute Common Terminology Criteria for Adverse events version 5.0 (NCI CTCAE v. 5.0) will be used for all grading. A dose limiting toxicity (DLT) is defined as an adverse event or abnormal laboratory value assessed as grade 3 or greater that is not clearly due to the underlying disease or extraneous causes with the following exceptions:

- Grade 3 nausea/vomiting or diarrhea for less than 72 hours with adequate antiemetic and other supportive care.
- Grade 3 fatigue for greater than 1 week.
- Grade 3 or higher electrolyte abnormality that lasts up to 72 hours, is not clinically complicated, and resolves spontaneously or responds to conventional medical interventions.
- Grade 3 or higher amylase or lipase that is not associated with symptoms or clinical manifestations of pancreatitis.
- Grade 3 neutropenia.
- Grade 3 thrombocytopenia without clinically significant bleeding.

For the Dose Finding Phase of the study, the dose will be deemed tolerable if no DLTs occurs within the first 4 weeks of progesterone treatment. Prior to enrolling patients into a higher dose level, CTCAE grade ≥ 2 adverse events will be reviewed for all patients at the current dose level.

Management and dose modifications associated with adverse events are outlined in **Section 5.4**.

Dose escalation will proceed to different dose levels according to the scheme presented earlier (**Section 5.2**).

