5.4 Dose Modification

Progesterone will be withheld for any instance of a CTCAE v5.0 grade 3 or greater toxicity (except for grade 3 neutropenia or grade 3 thrombocytopenia without clinically significant bleeding). Drug may be resumed, at the discretion of the treating physician, if the toxicity has reduced to the grade 0-1 level within 14 days. Treatment will be discontinued if toxicity persists beyond 14 days. For toxicity not clearly due to the underlying disease or extraneous causes, 50% dose reduction of original dose will be used when resuming treatment after sufficient recovery of toxicity as defined above. If toxicity is clearly due to the underlying disease or extraneous causes, no dose reduction is required after sufficient recovery of toxicity as defined above. Treatment will also discontinue if there is development of a DLT after one dose reduction.

Progesterone will be discontinued if patient develops any specific contraindication for use of progesterone (e.g. thromboembolic event). The treating physician can also stop progesterone if he/she feels that doing so would be in the best interest of the patient.

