- **Inpatient hospitalization or prolongation of existing hospitalization** - Hospitalization admissions and/or surgical operations scheduled to occur during the study period, but planned prior to study entry are not considered AEs if the illness or disease existed before the patient was enrolled in the trial, provided that it did not deteriorate in an unexpected manner during the trial (eg, surgery performed earlier than planned).
- **A persistent or significant disability/incapacity** or substantial disruption of the ability to conduct normal life functions, or a **congenital anomaly/birth defect**.
- **Important medical events** that may not result in death, be life-threatening, or require hospitalization may be considered serious when, based upon appropriate medical judgment, they may jeopardize the participant and may require medical or surgical intervention to prevent one of the outcomes listed in this definition. (Examples of such medical events include allergic bronchospasm requiring intensive treatment in an emergency room or at home, blood dyscrasias or convulsions that do not result in inpatient hospitalization, or the development of drug dependency or drug abuse).

Classification of an Adverse Event

Severity of Event

Most adverse events (AEs) will be graded according to Common Terminology Criteria for Adverse Events (CTCAE) version 5.0 (grade 1-5). For AEs not included in CTCAE, the following guidelines will be used to describe severity to match the CTCAE grading scale.

- **Mild** – Events require minimal or no treatment and do not interfere with the participant's daily activities.
- **Moderate** – Events result in a low level of inconvenience or concern with the therapeutic measures. Moderate events may cause some interference with functioning.
- **Severe** – Events interrupt a participant's usual daily activity and may require systemic drug therapy or other treatment. Severe events are usually potentially life-threatening or incapacitating. Of note, the term "severe" does not necessarily equate to "serious".
- **Life-threatening** – Events result in the patient being at immediate risk of death from the reaction as it occurred.
- **Death**

Relationship to Study Intervention

All adverse events (AEs) must have their relationship to study intervention assessed by the clinician who examines and evaluates the participant based on temporal relationship and his/her clinical judgment. The

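### In the expansion, from the fourth counted patient one treatment-related death alone cannot trip the 33% toxicity rule, and no visible text makes enrolment wait for DSMC review

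*Combined protocol and SAP*

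**What the plan says.** Section 5.2 promises ongoing review in Part 2: "Continuous evaluation of toxicity events in the cohort expansion will be performed throughout enrollment in the expansion cohort". The rule attached to that review appears in 5.2 and again under Safety assessment in 15.1: "If, at any time, the aggregate rate of treatment-related toxicities meeting DLT criteria exceeds 33% across all subjects treated in the expansion cohort", then "the findings will be discussed and further enrollment may be interrupted". Neither place names who discusses the findings or who decides. The nature and grade of the toxicity are weighed only afterwards, when a new dose is considered.

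Section 5.3 counts the following as a DLT, apart from a list of exemptions: "adverse event or abnormal laboratory value assessed as grade 3 or greater that is not clearly due to the underlying disease or extraneous causes". Section 16 grades events 1 to 5, with death as grade 5.

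On cohort size, 15.1 says: "A total of 20 patients will be enrolled at the MTD (including those in the Dose finding phase at this dose level". The toxicity rule refers to subjects treated in the expansion cohort and does not say whether the dose-finding patients are in its denominator.

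Section 16 provides these routes after a death:
- Every serious adverse event goes to the drug supplier's safety unit within 24 hours, whatever its cause.
- An SAE form is completed, and the PI determines what is reported to the IRB, DSMC and FDA.
- Unexpected fatal suspected reactions go to the FDA within 7 calendar days.
- The IRB makes the final determination on unanticipated problems.
- The study team reviews toxicity monthly and reports to the DSMC at appropriate times.
- Routine DSMC review is every 6 months or annually, depending on risk level.

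**The concern.** A pooled rate is a reasonable limit on tolerability. It is a poor detector of one very serious event, because it needs several events before it reacts and gives a death no extra weight. Safety is a primary objective, and most patients at the chosen dose enter after dose finding: 20 - 6 = 14 to 20 - 3 = 17. Under the rule as written, they may keep entering after a death attributed to progesterone, with no requirement that an independent committee first decide whether that is acceptable.

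The adverse reaction table in section 13 lists no fatal reaction, so the event is probably rare. It is not excluded in principle. Section 5.4 says: "Progesterone will be discontinued if patient develops any specific contraindication for use of progesterone (e.g. thromboembolic event". Section 9 lowers that risk by excluding patients with active or recent thromboembolic disease.

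**Working it through.** **Plan's own figure.** The 33% is a chosen limit. The documents give no error rate or stopping probability for it, so there is nothing to reproduce.

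**Inputs.** Threshold above 33% (5.2, 15.1). Cohort of 20 including dose-finding patients at that dose (15.1). Three to six such patients, with 0 of 3, 1 of 6 or 2 of 6 DLTs (rules in 5.2). Accrual of 1-2 a month (section 9). I count at most one event per patient.

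**Events needed.** The smallest r with r/n > 0.33 is:

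| n | 1-3 | 4-6 | 7-9 | 10-12 | 13-15 | 16-18 | 19-20 |
|---|---|---|---|---|---|---|---|
| r | 1 | 2 | 3 | 4 | 5 | 6 | 7 |

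At 20 patients, 6/20 = 30% is still below the limit.

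**One related death in a new patient, with no other new event:**

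| Who counts | Running rate | Rule silent at |
|---|---|---|
| All 20, from 0 of 3 | highest 1/4 = 25% | 17 of 17 positions |
| All 20, from 1 of 6 | highest 2/7 = 28.6% | 14 of 14 |
| All 20, from 2 of 6 | 3/7, 3/8 and 3/9 exceed; 3/10 = 30% does not | 11 of 14 |
| Only 17 new patients | 1/1, 1/2 and 1/3 exceed; 1/4 does not | 14 of 17 |
| Only 14 new patients | as above | 11 of 14 |

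From 2 of 6 the rate already exceeds 33%, read literally (2/6 = 33.3%), before anyone new enters. If 33% is read as exactly one third, the third, sixth, ninth (and so on) patient needs one more event, and the conclusion is unchanged.

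**Patients entering before someone looks.**
- Before the next monthly team meeting: 1 × (1 to 2) = about 1-2.
- Before a six-monthly DSMC review, if the death is not brought to the DSMC sooner: 6 × (1 to 2) = 6-12, an upper bound. An annual review would give 12-24, limited by the 14-17 who remain.
- If the futility rule stops enrolment at 10 at that dose: 10 - 6 = 4 to 10 - 3 = 7 new patients in all. The text does not say whether enrolment pauses while the 8-week scans are awaited.

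**How often a hold would occur.** The documents give no related-death rate, so 1% and 2% are assumptions. P(at least one) = 1 - (1 - p)^n:

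| New patients | p = 1% | p = 2% |
|---|---|---|
| 14 | 13.1% | 24.6% |
| 17 | 15.7% | 29.1% |
| 4 (futility stop) | 3.9% | 7.8% |
| 7 (futility stop) | 6.8% | 13.2% |

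**The case against.** The strongest reply is that a related death would not go unseen. The supplier hears within 24 hours. Section 13 lists no fatal reaction and section 16 judges expectedness partly by severity, so the death would very likely count as unexpected and reach the FDA within 7 days, with an assessment going to the IRB. All three bodies are outside the study team. The team itself meets monthly, and section 5.1 lets the institution terminate the trial. All of this stands. A reader might infer from the 33% rule that nobody independent would look promptly, and the documents do not support that. What remains is narrower: none of these routes makes enrolment wait, and reporting to the DSMC depends on the PI's determination.

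A reader might also infer that Part 2 dropped a safeguard present in Part 1, where enrolment at the next dose level "will only start after data is presented to the Winship Data Safety Monitoring Committee (DSMC) and final approval is obtained". That gate governs moves between dose levels. It is not tied to a death, and Part 1 states no hold within a level either.

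A third tempting reading is that all 14-17 remaining patients would be exposed. That requires full accrual, no futility stop, and no action by anyone before an annual review.

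Finally, the institutional monitoring plan cited in section 16 is not in the documents and could contain an ad hoc hold. That limits the point to the protocol text.

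**Conclusion.** The point holds as a statement about the protocol text. The only stated trial-level toxicity trigger in the expansion gives a related death the weight of one grade 3 event, and even when tripped it leaves interruption optional. If the dose-finding patients count and had 0 of 3 or 1 of 6 DLTs, the rule is silent for a single related death in any new patient. If only new patients count, it can fire on such a death only among the first three. These counts need no assumed death rate.

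The practical size is modest. The event is probably rare, outside bodies are told quickly, and about 1-2 patients would enter before the next monthly meeting. The 6-12 figure is an upper bound under six-monthly review and falls if futility stops enrolment. The documents do not show that a death would escape notice or that no hold exists anywhere. They show that the protocol does not state one. This is a cheap improvement worth making.

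**What to change.** In 5.2 and 15.1, add: any death assessed as at least possibly related to progesterone on the section 16 scale, from first dose through 28 days after the last dose, suspends new enrolment until the DSMC has reviewed it and recorded whether enrolment may resume, whatever the running rate. Keep the 33% rule, with deaths still counted in it. If the institutional plan already contains such a hold, a cross-reference is enough.

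State also that deaths from documented progression do not trigger the hold. Section 16 conflicts here: under Serious Adverse Event Reporting, death from any cause goes on an SAE form, while under Adverse Event Reporting, documented fatal progression is not to be reported as a serious event.

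The cost is one or two sentences in two places and an ad hoc review by the existing committee. An assumed pause of 2-4 weeks at 1-2 patients a month delays about 0.5 × 1 = 0.5 to 1 × 2 = 2 enrolments. The trigger still rests on causality as "assessed by the clinician who examines and evaluates the participant" (section 16), so a death called unlikely related would not reach the DSMC by this route.
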